Expansion into a multi-site protocol: In its first year, the study experienced initial delays as the software necessary for IMT was upgraded to be compatible with newer versions of Windows as well as the VA system. Moreover, even after enrollment began, recruitment of systolic HF patients was more difficult than projected. In response to this challenge, the study will be expanded to multiple sites as well as home based exercise session, each with enhanced recruitment and adherence strategies. This change in study design coincides with [name] plans to transition to the VA Pittsburgh Healthcare System (VAPHS) which will be used to the advantage of the protocol design.

1. [name] will continue as PI of the overall trial as well as site PI at the (VAPHS). Four training arms (Aerobic vs. Strength vs. Combined aerobic-strength, vs. IMT) will be completed at VAPHS, along with pre- and post- skeletal muscle biopsies, bloodwork, DXA and functional assessments. 100 HF patients will be enrolled at that campus, drawing from its robust HF program as well as its extensive HF telehealth database (see recruitment strategies below).
2. The study will also continue at the VABHS where enrollment goals will be 50 HF patients. [name] will assume responsibility as the Boston site PI. Exercise randomization at the VABHS will be limited to aerobic vs. IMT, both to increase efficiencies for the reduced staffing available once [name] and members of his staff have departed for Pittsburgh, and also to ensure adequate enrollment to a RR&D SPIRE-funded 1 I21 RX001423-01A1 substudy (Exercise Training in HF: Structural and Functional Cardiac Remodeling [PI-[name]]) which will explore correlative effects of IMT vs. aerobic training on cardiac remodeling. Also, given [name] role as principal investigator in the ancillary SPIRE study of exercise effects on cardiac remodeling as well as the distinctive skillset required for the echo-based analysis of skeletal muscle perfusion (that is part of the original protocol), both the perfusion and remodeling ultrasound assessments will be studied exclusively at the VABHS. This too is a decision to help maximize local enthusiasm for the protocol, as it becomes a distinctive VABHS goal and responsibility.

Table 4: Outline of protocol (by visit)

Initial Assessment	Visit 1	Informed consent and physical exam, physical functional assessment battery (aerobic, strength, 6MWT, Hand Grip, gait speed, Sit to Stand, and questionnaires)

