	Visit 2 (within one week of visit 1)	Skeletal muscle biopsy; Serology and DXA scan Randomization
	Visit 3 (2-3 days after visit 2) (VABHS only)	Reassessment of biopsy site
Exercise Training	Visits 3/4-38/39	Exercise training sessions (3X/weekly; 60 minutes; 12 weeks)
Post assessment	Visit 39/40-41/43	Post-exercise assessment battery and additional group of assessments completed at visits 1 to 2/3

Table 5: Expansion to a Multi-Site Trial

	Recruitment goals	Exercise arms
VAMC Pittsburgh	100	Aerobic (35), Combined aerobic-strength (30 enrollees), IMT (35 enrollees)
VAMC Boston	50	Aerobic (25 enrollees); IMT (25 enrollees)

Total: 150 HF patients: Aerobic—60; IMT—60; Combined—30;

Study Population

• ***Study Population:*** 150 male and female systolic HF patients with mild-moderate symptoms while on optimal medical therapy will be enrolled. This target will allow for adequate power to address the study objectives even after accounting for a 20% drop-out rate due to attrition and/or suboptimal tissue samples for genetic analysis. Given the expansion to two campuses, and the variation in randomization at each site, the overall proportions of patients enrolled will vary from the original study design but still provide a sound statistical foundation for the anticipated analyses (see statistics section below).

• HF diagnosis will be contingent on a previous hospitalization for HF or physician assessment of HF associated. Each candidate will be examined at the time of enrollment by a cardiologist to ensure that he/she is clinically stable.

• ***Inclusion Criteria:***

- NYHA class II or III for the previous three months despite a minimum of 6 weeks of optimal treatment

- Age \geq 50 years

- Left ventricular EF (LVEF) (by echocardiogram or radionucleotide imaging study within 12 months of enrollment).

- Optimal therapy according to AHA/ACC and HFSA HF guidelines, including treatment with ACEI and beta-blocker therapy (for at least 6 weeks), or have documented reason for variation, including medication intolerance, contraindication, patient preference, or personal physician's judgment.

✓ Patients using aspirin (ASA) will be eligible, but asked to hold the medication for 48 hours prior to biopsy. This technique has previously been used with consistent safety. Patients will also be asked to avoid non-steroidal anti-inflammatory medications (NSAIDs) for 48 hours prior to the biopsy.

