a) *Aerobic vs. Strength vs. Aerobic-Strength regimens will be compared to one another b) Inspiratory Training will be compared to Aerobic-Strength:* In this aim, we compare the combined aerobic-strength training regimen to the single-therapy regimens of aerobic training and strength training, as well as the inspiratory training regimen. These comparisons will be made with changes in the functional outcomes (peak VO₂, 1RM) from baseline as the continuous outcome measures in separate models and training regimen as the categorical predictor in a general linear model, with the following factors considered as potential confounder variables: age, sex, and comorbidities. To limit the type I error rate, only the pre-planned comparisons of the combined aerobic-strength training to the other regimens will be considered. In addition, secondary analyses will consider the following aerobic, strength and inspiratory variables as outcome variables in similar analyses to those outlined above: 6MWT, sit-to-stand, and hand grip strength.

- **Aim 2. To assess gene expression and skeletal muscle perfusion in relation to the different training regimens:** In this aim, we examine the change from baseline to post-exercise regimen in the expression of proteolytic (FoxO and Ubiquitin) and anti-proteolysis (IGF-1 and PGC-1 α) genes as predictors of the change in functional outcomes (peak VO₂, 1RM) over the same period. Separate general linear models for each functional outcome will be performed with gene expression changes as the primary predictor and the following variables considered as potential confounders: age, sex, and comorbidities. As above, a 10% rule for introducing confounding variables and the transformation of outcome variables to deal with regression assumption violations will be considered.

Treatment regimens will also be categorized as those with and without direct skeletal muscle stimulation and this categorical variable will be considered as a predictor of a change in the expression of proteolytic and anti-proteolysis genes in general linear models in a similar fashion to that described above. In addition, similar general linear models will be used with changes in skeletal muscle perfusion as a continuous outcome and aerobic and inspiratory training vs. strength-only training as a categorical predictor with similar potential confounders as noted above.

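### The Aim 2 perfusion contrast (aerobic and inspiratory vs strength-only training) cannot be estimated, because the only site measuring perfusion randomises no strength-only patients

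*Combined protocol and SAP*

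**What the plan says.** The Aim 2 paragraph of the statistics section specifies general linear models with "changes in skeletal muscle perfusion as a continuous outcome and aerobic and inspiratory training vs. strength-only training as a categorical predictor", using the same potential confounders as the other Aim 2 models. Perfusion is also in the title of Aim 2.

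The section on expansion into a multi-site protocol then fixes where perfusion is measured and who can be randomised there:

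- On measurement: "both the perfusion and remodeling ultrasound assessments will be studied exclusively at the VABHS". The reason given is the special skill needed for the "echo-based analysis of skeletal muscle perfusion (that is part of the original protocol").
- On allocation: "Exercise randomization at the VABHS will be limited to aerobic vs. IMT".

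Table 5 gives the numbers. Boston has "Aerobic (25 enrollees); IMT (25 enrollees"). Pittsburgh (VAPHS) has "Aerobic (35), Combined aerobic-strength (30 enrollees), IMT (35 enrollees"). The Sample size/Power paragraph names the same two Boston arms.

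The secondary analyses after Aim 2 also use change in perfusion, alongside change in gene expression, as a predictor of function and quality of life.

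**The concern.** The contrast needs perfusion measurements in patients who trained for strength only. Perfusion is measured at one site, and that site randomises to two regimens that both belong to the other side of the contrast. The problem is therefore not low power: the comparison has no second group.

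Software given a constant predictor drops the term or reports no estimate, so the failure would be visible and would not yield a wrong number unnoticed. The risk lies in what follows. Boston can support a randomised aerobic vs IMT comparison of perfusion, but I found no such comparison specified. If the gap is noticed only at analysis, a substitute will be chosen when the perfusion data are already available, and it will be post hoc for an outcome named in an aim.

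**Working it through.** **1. Planned patients by site and arm (Table 5).**

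| | Aerobic | IMT | Combined | Strength-only | Total |
|---|---|---|---|---|---|
| Pittsburgh | 35 | 35 | 30 | 0 | 100 |
| Boston | 25 | 25 | 0 | 0 | 50 |
| Both | 60 | 60 | 30 | 0 | 150 |

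The sums agree with the totals printed under the table.

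**2. Estimability of the written contrast.** Let x = 1 for aerobic or inspiratory training and x = 0 for strength-only, in the model: change in perfusion = b0 + b1·x + confounders. On the 50 planned Boston patients, x = 1 in every row, so the column for x equals the intercept column. The matrix of intercept and x has rank 1 of 2, and b1 is not estimable. Equivalently, the variance of a two-group difference is proportional to 1/n1 + 1/n0, and n0 = 0. Adding confounders does not help, because they put no variation into x.

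**3. Dependence on the arm list.** The documents disagree about a strength arm. Overall Study Protocol, Table 5 and the Exercise Training section give three arms without one. Item 1 of the multi-site section lists four arms including Strength, to be run at VAPHS. Sample size/Power states four arms but then names only aerobic, combined and IMT. On the four-arm reading, strength-only patients exist at Pittsburgh but have no perfusion measurement. On the three-arm reading, they exist nowhere. The Boston count is zero either way. Combined training is also absent from Boston and cannot stand in.

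**4. Dependence on the sample size.** Sample size/Power and Limitations give an overall target of 210, against 150 in Overall Study Protocol, Study Population and Table 5. This changes denominators but not the two arms available in Boston.

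**5. Precision of the comparison Boston can support.** With x = 1 for aerobic and 0 for IMT, the matrix has rank 2 of 2, so the effect is estimable. The detectable difference in SD units (80% power, two-sided 5%) is approximately (1.960 + 0.842) × √(2/n) with n per arm; the t-test value is slightly larger.

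- The plan's own figure first: n = 40 gives 2.802 × 0.2236 = 0.626 (normal) and 0.634 (t-test), against 0.64 stated. The method reproduces it.
- n = 25: 2.802 × 0.2828 = 0.792 (normal), 0.809 (t-test).
- n = 20, that is 25 × (1 − 0.20): 2.802 × 0.3162 = 0.886 (normal), 0.909 (t-test).

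The 95% confidence interval half-width is t(0.975, 2n − 2) × √(2/n): 0.569 SD at 25 per arm and 0.640 SD at 20 per arm.

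**The case against.** **Early Boston patients.** The multi-site section says that "even after enrollment began, recruitment of systolic HF patients was more difficult than projected", so Boston was randomising before the redesign, and some of those patients may have been allocated to strength training and had perfusion measured. This stands as a caveat. The documents give no count, do not say which arms Boston used then, and do not say how such patients would be analysed. The point is therefore limited to patients randomised under the current plan.

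**Size of the harm.** The analysis is subsidiary. The opening of Materials and Method lists perfusion among related differences, the Aim 2 power statement concerns gene expression only, and General considerations says isolated results will not be given undue weight. All of this is fair and keeps the point modest. It does not make the planned model work.

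**The 0.91 SD figure.** The 20% loss is described as a "20% drop-out rate due to attrition and/or suboptimal tissue samples for genetic analysis". The tissue-sample part does not apply to ultrasound, so 20 vs 20 may overstate the loss. The documents also give no separate sample size for perfusion; 50 is the Boston enrolment goal, and fewer patients may be measured. The figures are indicative. Nor did the plan attach its generic 0.64 SD to perfusion, so missing it is not a failure against a stated target.

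**Stronger readings that a reader might infer.** One is that the trial has no strength-only arm at all, so that measuring perfusion in Pittsburgh could not help. Table 5 suggests this, but item 1 of the multi-site section says otherwise, so it is not established. Another is that Aim 2 as a whole fails. It does not, because the gene-expression models do not need perfusion. A third is that perfusion has been dropped. The pre/post battery, the visit table and the assessment methods describe no perfusion procedure, yet Materials and Method, the multi-site section, Aim 2 and the secondary analyses all retain it. That is a question for the sponsor, not a finding.

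**Conclusion.** The point holds. Under the current design, the Aim 2 comparison of perfusion between aerobic plus inspiratory training and strength-only training has no patients on the strength-only side and gives no estimate. The conclusion rests on two explicit statements, that perfusion is measured only in Boston and that Boston randomises only to aerobic or IMT. It does not depend on which arm list or overall sample size is correct.

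The consequence is limited to the perfusion part of Aim 2 and to the secondary model that uses perfusion as a predictor. That model can draw only on Boston patients, 50 if the enrolment goal is met, which the plan does not say. The Aim 1 comparisons of peak VO₂ and 1RM are untouched. This should be fixed, but it does not threaten the trial's main comparisons.

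**What to change.** First, the sponsor confirms whether perfusion is still measured at VABHS.

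**If it is**, then before any perfusion data are examined:

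- Replace the contrast with one the design can support. One option: *Change in skeletal muscle perfusion will be compared between aerobic and inspiratory training among patients randomised at VABHS, in a general linear model with the same potential confounders.* A descriptive report of change within each arm is another option; the choice is the sponsor's.
- Say openly that aerobic vs inspiratory training is a different question from the contrast now in Aim 2, which pools those two regimens.
- State the precision: at best about 0.81 SD detectable with 80% power (25 vs 25), or 0.91 SD at 20 vs 20 if the plan's 20% loss applies.
- Say how any Boston patients randomised to another arm before the redesign will be handled.
- State that the secondary model of gene expression and perfusion uses Boston patients only.

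**If it is not**, delete the contrast and remove perfusion from Aim 2 and from the secondary model.

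The cost is a few sentences of the plan, with no new patients, visits or measurements. The three-arm and four-arm lists also need to be reconciled, but that is a separate correction and would not by itself repair this contrast.

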Standard histological techniques will be employed to analyze cross-sectional area of muscle fibers, as well as damage, inflammation, and atrophy. Histochemistry will be performed to differentiate type I from type II fibers (cytochrome C oxidase activity). Additionally immunohistochemistry using monoclonal antibodies specific to the MHC isoforms will be used to assess the hybrid skeletal muscle types. These histomorphometric and enzymatic parameters will be correlated to atrogene expression to delineate whether specific gene expression patterns translate into pertinent physiological changes, as well as changes in exercise performance.

In addition, standard measures of aerobic enzymes (citrate synthase) will be completed to establish correlations to functional parameters and associated signaling patterns. Citrate synthase will be assayed spectrophotometrically from skeletal muscle biopsies.

Serum analyses: To be completed at the same time of the muscle biopsy. A core of study nurses are available at the CSU to complete the phlebotomy required. Serum will be obtained from all individuals in this study. Standard phlebotomy technique in sterile fashion will be utilized. Whole venous blood samples will be centrifuged at the CSU for 10 min at 4C. Samples will be put into dry ice and transported to freezer storage at the JP campus. Serum will be stored at -80C until batch analyses are completed. Serum analyses will be completed at the VABHS laboratories.

Assays will be completed that are pertinent to the secondary analyses of this investigation. Insulin, CRP, IL-6, IL-1, IL-1 receptor, TNF- α , TNF α receptor, Cortisol, Adiponectin (high molecular weight and total), Glucose, electrolytes, and liver function serology will all be assessed

Dual energy x-ray absorptiometry (DXA): DXA will be completed by [name]. A GE Healthcare Lunar iDXA Bone Densitometer 5th Generation instrument with encore software version 13.6 is available for these assessments. A total body scan will be used to determine total body fat free mass and regional body composition (107). Subjects will lay flat on their back on an open table for 15 minutes while a bar passes over them. Using these DXA-based measurements, CPX performance indices will be normalized to fat free mass, thereby eliminating confounding effects of body fat. This will modify the tendency to underestimate performance among those who are overweight.

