General considerations: The analyses described below are of continuous outcome measures, primarily changes in function outcomes and gene expression and either continuous or categorical predictors. All analyses will be performed as general linear models. Potential confounders of each analysis will be outlined below and a 10% rule for evaluating confounders will be used, namely including a potential confounder if a 10% or greater change is seen in the main predictor effect. In all instances, outcome variables will be evaluated for violation of regression assumptions and transformation of these variables will be considered as a remedy if needed. Analyses will generally be performed with an intent-to-treat approach, with sensitivity analyses performed to assess the role of drop-outs on the results.

This grant examines a complex interplay of exercise regimens, gene expression and functional measures, resulting in a number of hypotheses that require testing. We are cognizant of the role of type I error in this and in interpreting results, focus will be placed on the overall results of these analyses and not on the results of individual tests. Thus, for example, significant relationships among gene expression outcomes and treatment categories as a whole will be considered as support for these hypotheses and isolated significant associations will not be unduly weighted in the interpretation of results.

Randomization will be generated using a SAS program based upon permuted random blocks of variable size to assure approximate balance over time and will be stratified by sex and statin use.

Validation of Study Measurements: At the start of the study, there will be two assessments of physical function battery. Intraclass correlations will be used to determine the relative repeatability of the various components of the battery. This information will be included in all manuscripts using these measures.

- *Aim 1. To assess differences in functional outcomes (peak VO₂, 1RM) relative to the training therapy:*

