Secondary analyses will include assessment of the relative impact of changes in skeletal gene expression vs. changes in perfusion dynamics as predictors of changes in function and quality of life as outcomes. Measures of changes from baseline in serum inflammation, cytokines, and adipokines, and effects of muscle histology will be included as covariates in these analyses. General linear models will be used (outlined above).

Sample size/Power: In this study, we plan to recruit 210 individuals and assign them to one of 4 treatment arms, i.e., randomized between aerobic, aerobic strength, and IMT in VAPHS and between aerobic and inspiratory muscle training in Boston. Sample size calculations are based on 20% attrition over the course of the study. In general, a sample size of 40 per group, using a t-test of independent samples as a simplified model, results in an effect size of 0.64 SD units for 80% power, using a two-sided alpha of 5%.

- **Aim 1:** For this aim, we present calculations for detecting differences in peak VO₂. Previous work by Becker (108) shows a $2.1 \text{ mL O}_2 \cdot \text{kg}^{-1} \cdot \text{min}^{-1}$ change in peak VO₂ in a 6 month aerobic-strength training regimen. Similarly, Tyne-Lenne, et al. shows a $1.1 \text{ mL O}_2 \cdot \text{kg}^{-1} \cdot \text{min}^{-1}$ change in a strength-only regimen (109), HF-ACTION (85) shows a $0.6 \text{ mL O}_2 \cdot \text{kg}^{-1} \cdot \text{min}^{-1}$ change in an aerobic regimen and the IMT trial by Dall'Ago et al. (12) shows a $4 \text{ mL O}_2 \cdot \text{kg}^{-1} \cdot \text{min}^{-1}$ change with inspiratory training. Standard deviations [SD] of the change in peak VO₂ over an exercise regimen are not directly available but using interquartile range values from the largest study [HF-ACTION, n=1442], we obtain a SD value of 2.2 for a 3-month intervention. This would correspond to detecting a difference of $1.26 \text{ mL O}_2 \cdot \text{kg}^{-1} \cdot \text{min}^{-1}$ in any comparison with 80% power, assuming a SD=2.2.

- **Aim 2:** In a similar fashion, a simplified comparison of those with gene expression below the median vs. those above the median would be able to detect a difference of $1.26 \text{ mL O}_2 \cdot \text{kg}^{-1} \cdot \text{min}^{-1}$ in peak VO₂ with 80% power. Analyses of combined training groups facilitates capacity to detect smaller differences between groups.

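### The secondary gene-versus-perfusion model conditions on muscle histology, a step on the gene pathway in the protocol's own account, and sets no limit on covariates for about 40 patients

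*Combined protocol and SAP*

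**What the plan says.** The last paragraph of Aim 2 in the statistical section plans secondary analyses. Their stated target is: "relative impact of changes in skeletal gene expression vs. changes in perfusion dynamics as predictors of changes in function and quality of life as outcomes". On adjustment it says: "Measures of changes from baseline in serum inflammation, cytokines, and adipokines, and effects of muscle histology will be included as covariates in these analyses". It then refers back to the general linear models described earlier.

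The wording is firmer than elsewhere. In Aim 1 and the main Aim 2 models, age, sex and comorbidities are only candidates, screened by the rule under General considerations: "including a potential confounder if a 10% or greater change is seen in the main predictor effect". The secondary paragraph gives no marker list, no maximum, no composite score and no order of entry.

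On the sample, the section on expansion to several sites says that "both the perfusion and remodeling ultrasound assessments will be studied exclusively at the VABHS". It also says: "The study will also continue at the VABHS where enrollment goals will be 50 HF patients". The Study Population section claims adequate power "even after accounting for a 20% drop-out rate due to attrition and/or suboptimal tissue samples for genetic analysis".

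On the role of histology, the section on muscle histology and morphometry says the histological and enzymatic measures will be correlated with atrogene expression "to delineate whether specific gene expression patterns translate into pertinent physiological changes".

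**The concern.** Two problems follow, and they are separable.

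The first is over-adjustment. In the protocol's account, gene signalling alters muscle fibres and altered fibres change function. A gene coefficient conditional on histology therefore measures only the part of the gene effect that bypasses muscle structure. A perfusion effect that bypasses fibre structure keeps its full size in the same model. A comparison meant to say which predictor matters more is then weighted against genes. One histology covariate is enough to cause this.

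The second is model size. Any model containing perfusion is confined to Boston, and the covariates are named by class without limit. Depending on how the sentence is carried out, the model may have fewer than three patients per predictor. R-squared and the ranking of predictors would then be unstable.

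At stake is what this secondary analysis can conclude. A small gene coefficient could mean that genes matter little, or that their consequence was held fixed.

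**Working it through.** **The plan's own figure.** The only general power statement is 0.64 SD with 40 per group, two-sided 5% alpha and 80% power. It reproduces: a two-sample t-test with 40 per group detects 0.634 SD, and power at 0.64 SD is 80.7%. It does not describe the model at issue, which has about 40 patients in total and for which no power is stated.

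**Evaluable patients.** Boston goal 50, loss 20%: 50 × 0.80 = 40.

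**Candidate predictors (a reading of the assay and histology sections, so an assumption).**
- Serum, in the three named classes: CRP, IL-6, IL-1, IL-1 receptor, TNF-α, TNF-α receptor and two adiponectin measures = 8. Insulin, cortisol, glucose, electrolytes and liver tests fall outside those classes.
- Histology: cross-sectional area, damage, inflammation, atrophy, type I/II fibres and hybrid fibre type = 6.
- Genes: FoxO, ubiquitin, IGF-1 and PGC-1α = 4, or one if entered singly. Perfusion = 1.

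**Effect of model size.** For n patients and k predictors, the residual df are n − k − 1. The expected R-squared when nothing is related is k/(n − 1). The SE factor against k = 2, for uninformative and uncorrelated covariates, is √[(n − 4)/(n − k − 2)]. With n = 40:

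| Model | k | df | Patients per predictor | Chance R² | SE factor |
|---|---|---|---|---|---|
| One gene, perfusion | 2 | 37 | 20 | 2/39 = 0.05 | 1.00 |
| + one composite for each of 4 classes | 6 | 33 | 6.7 | 6/39 = 0.15 | 1.06 |
| Same, four genes | 9 | 30 | 4.4 | 9/39 = 0.23 | 1.11 |
| One gene, perfusion, 14 separate markers | 16 | 23 | 2.5 | 16/39 = 0.41 | 1.28 |
| Same, four genes | 19 | 20 | 2.1 | 19/39 = 0.49 | 1.38 |
| Same, plus age, sex, one comorbidity term | 22 | 17 | 1.8 | 22/39 = 0.56 | 1.50 |

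The smallest partial correlation detectable with 80% power (Fisher z) rises from 0.44 at k = 2 to 0.61 at k = 22.

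Sensitivity of the marker-by-marker range:
- With no loss (n = 50), chance R-squared is 16/49 = 0.33 to 22/49 = 0.45.
- With a further 20% lost (n = 32, an assumption), it is 16/31 = 0.52 to 22/31 = 0.71.
- Counting four histology measures instead of six, at n = 40, it is 14/39 = 0.36 to 20/39 = 0.51.

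**Effect of conditioning on histology.** Let histology change = a × gene change + error, and function change = c × gene change + b × histology change + error. The total gene effect is c + ab. Adjusting for histology leaves c = total × (1 − s), where s is the share carried by histology. For an assumed total of 0.50:
- s = 25%: 0.50 × 0.75 = 0.375
- s = 50%: 0.50 × 0.50 = 0.25
- s = 75%: 0.50 × 0.25 = 0.125, about 0.13
- s = 100%: 0

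A large simulation agreed with these values.

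**Would the 10% rule prevent this?** No. Adding the mediator moves the gene coefficient by the fraction s, so the rule would admit any histology measure carrying 10% or more of the effect.

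**Serum inflammation is different.** The background on exercise and proteolytic gene expression describes the inflammatory milieu as a possible inducer of gene expression differences, so it sits upstream. Assume, in standardised units, a slope of 0.5 from inflammation to gene expression and a direct effect of 0.2 of inflammation on function. The unadjusted gene coefficient is then 0.50 + 0.2 × 0.5 = 0.60, and adjustment returns it to 0.50. With no direct effect it is 0.50 either way.

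**The case against.** The strongest reply is that the text names classes, not every assay, and does not say that each marker enters separately. The Limitations section mentions that the statistician is exploring factor analysis, so composites are plausible. That stands as far as model size goes: a reader might infer that all serum and histology markers must enter, and the text does not say so. But no composite is specified, and a histology composite is still a mediator.

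It can also be said that the reference back to the earlier models may bring in the 10% rule. That is possible, but the rule would select a mediator rather than exclude it.

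A reader might infer that the serum covariates also adjust the pathway away. The documents do not support this, because their account puts inflammation ahead of gene expression. Serum adjustment may be legitimate control of confounding, and dropping it altogether could introduce bias.

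The main Aim 2 models already relate gene change to peak VO₂ and 1RM without histology and without restriction to Boston, and the link from genes to histology is to be examined by correlation. A conditional effect can also be a legitimate target. All this stands and limits the damage. It does not make the conditional model a fair comparison of overall impact, and the plan does not say that a direct effect is what it wants.

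Finally, General considerations says isolated significant findings will not be given undue weight. That guards against over-reading single tests; it does not correct a shifted coefficient.

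**Conclusion.** The concern holds for histology and, conditionally, for model size. Followed as written, the model removes whatever share of the gene effect runs through muscle structure: a quarter to all of it over the range shown. The true share is unknown. A reader might infer that the gene effect would vanish, but that needs complete mediation, which the documents do not assert.

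Overfitting depends on implementation: severe with separate markers (chance R-squared about 0.41 to 0.56), modest with composites (0.15 to 0.23). It would also be too strong to call the result mere noise. With a fixed covariate set the t-tests keep their nominal error rate; the harm is lost precision, inflated R-squared and an unreliable ranking.

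The conclusion rests on these assumptions:
- Genes and perfusion are compared in one model, hence in Boston patients only.
- The histology covariate is a change or post-training measure. If baseline histology was meant, the mediation argument falls and only model size remains.
- Histology carries more of the gene effect than of the perfusion effect; this determines the direction of the tilt.
- The marker counts are as read above, and no marker list stands in text absent from the version reviewed.

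This is a secondary analysis. Aim 1 and the main Aim 2 models are not affected.

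**What to change.** Reword the secondary-analysis paragraph of Aim 2 in three respects.

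1. Make the main version of this model change in gene expression plus change in perfusion, without histology. State that it uses Boston patients only and give the expected number.
2. Limit serum adjustment to a short list named in advance, or to one composite, with the reason for treating it as a confounder. With one gene measure, perfusion and one serum composite, k = 3 and chance R-squared is 3/39 = 0.08.
3. Report the histology-adjusted model separately, labelled as an exploratory mediation analysis, and say whether histology enters as baseline or change.

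The cost is wording, a slightly longer secondary analysis and less adjustment in the main version. No additional data are needed.
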